6.11. Bioanalytical and Pharmacokinetic Methods

Pharmacokinetic analyses will be conducted on patients who have received at least one dose of the study drug and have had samples collected to allow the estimation of abemaciclib PK parameters.

Plasma concentrations of abemaciclib and its major metabolites, LSN2839567 (M2) and LSN3106726 (M20), will be determined using a validated liquid chromatography/tandem mass spectrometry (LC/MS/MS) method.

Pharmacokinetic parameter estimates for abemaciclib and its major metabolites will be calculated by standard noncompartmental methods of analysis using Phoenix WinNonlin on a computer that meets or exceeds the minimum system requirements for this program. The primary parameters for analysis will be C_{max} , $AUC_{0-t_{last}}$ and $AUC_{0-\infty}$. Other noncompartmental parameters, such as $t_{1/2}$, $C_{L/F}$, and V/F may be reported. The PK profiles will be graphically presented and summary statistics of PK parameters will be obtained.

Additional exploratory analyses will be performed if warranted by data and other validated PK software programs (for example, NONMEM) may be used if appropriate and approved by Global Pharmacokinetic management. The version of any software used for the analysis will be documented and the program will meet the Lilly requirements of software validation.

6.12. Safety Analyses

6.12.1. Extent of Exposure

The number of cycles of treatment received, dose delays, and dose intensity will be summarized.

Extent of exposure will be measured by pill counts and summarized by cycle. The summary will include total dosage taken and dose intensity. Dose intensity will be calculated as the ratio of total dose taken to the assigned cumulative dose. The assigned cumulative dose for each patient during each cycle is 150 mg per dose \times 2 doses per day \times 28 days = 8400 mg for lower dose cohort and 200 mg per dose \times 2 doses per day \times 28 days = 11200 mg for the higher dose cohort. The assigned cumulative dose while on study for lower and higher dose cohort is 2×150 mg \times number of days and 2×200 mg \times number of days on treatment, accordingly.

Dose adjustments including the reasons for dose adjustment will also be listed and summarized.

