5.1. Summary of Study Design

This study is a multicenter, open-label, Phase 1 trial of abemaciclib in Chinese patients with advanced and/or metastatic cancers.

The study will be focused on safety evaluation and PK data collection in patients with all advanced and/or metastatic cancers. Patients will be randomized into 2 dose cohorts, and orally receive abemaciclib 150 mg or 200 mg every 12 hours (Q12H). One cycle is defined as 28 days (Cycle 1: 32 days), with modifications during Cycle 1 to enable PK sampling following a single dose and repeated doses. The treatment of abemaciclib will continue until disease progression, development of unacceptable toxicity, or fulfillment of the other discontinuation criteria. In case of patient discontinuation during Cycle 1, the enrollment will be extended until at least 10 patients with completed PK data accrued in each cohort. Analysis on available PK and safety data will be conducted after study completion.

All patients in the study receive at least 2 cycles of abemaciclib unless one or more of the criteria for discontinuation (refer to Protocol Section 6.3.1) are fulfilled; the short-term follow-up period for poststudy evaluation is 30 ± 7 days after the decision to discontinue treatment. [Figure JPBR 5.1](#) shows the study design for Study JPBR.

Abbreviations: Q12H = every 12 hours; R = randomization.

Figure JPBR 5.1 Study design for JPBR.

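### Section 6.12.1 sets two dose-intensity denominators that conflict with each other and with the 32-day Cycle 1, and the per-cycle one is not cut off when treatment stops

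*SAP*

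**What the plan says.** Section 6.12.1 defines the measure: "Dose intensity will be calculated as the ratio of total dose taken to the assigned cumulative dose". It also says at what level the measure is reported: "Extent of exposure will be measured by pill counts and summarized by cycle". Two denominators follow.

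- Per cycle: "The assigned cumulative dose for each patient during each cycle is 150 mg per dose", times two doses a day, times 28 days. The result is 8400 mg for the lower cohort and, in the same way, 11200 mg for the higher. No cycle is excepted.
- On study: "The assigned cumulative dose while on study for lower and higher dose cohort is" two doses of 150 mg or 200 mg, multiplied by the number of days on treatment. The SAP does not define those days.

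Section 5.1 describes the schedule to which these rules apply. Cycles last 28 days, except that the first lasts 32 and is run "with modifications during Cycle 1 to enable PK sampling following a single dose and repeated doses". The same section lets treatment run until progression, unacceptable toxicity or another discontinuation criterion, so a last cycle can end on any day. Section 6.8 uses the same 28-day figures for compliance, but there net of adjustments and of doses omitted or withheld.

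**The concern.** A dose-intensity ratio should read 100% for a patient who took every scheduled dose, and should fall only when doses are reduced, held or missed. Neither denominator guarantees this.

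The per-cycle rule takes no account of the four extra days of Cycle 1 or of its single-dose period, and it charges a full 28 days to a cycle that treatment discontinuation cut short. The on-study rule does count the extra days, but it charges full twice-daily dosing on each of them, including any single-dose PK day.

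Safety and tolerability are the primary objective, and section 5.2 plans for only 10 PK completers per cohort. In a by-cycle summary of 10 patients, nine at 100% and one at 50% because that patient's last cycle ended on day 14 give a mean of (9 × 100 + 50)/10 = 95%. No dose was reduced or held to produce that loss.

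**Working it through.** **Inputs.** Dose 150 or 200 mg, two doses a day, cycle length 28 days, Cycle 1 length 32 days (section 5.1); the two denominators (section 6.12.1). The SAP does not state the number of doses scheduled in Cycle 1, here called N. Base-case assumption: one single dose over the four extra days, then 28 days of twice-daily dosing, so N = 1 + 56 = 57.

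**1. The plan's own figures.** 150 × 2 × 28 = 8400 mg and 200 × 2 × 28 = 11200 mg. Both reproduce, for a 28-day cycle with two doses every day.

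**2. The two denominators compared on calendar days.** This needs no assumption about N. For the 150 mg cohort:

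| Completed cycles | Days | On-study rule (300 mg × days) | Sum of per-cycle rule | Gap |
|---|---|---|---|---|
| 1 | 32 | 9600 mg | 8400 mg | 1200 mg (14.3%) |
| 2 | 60 | 18000 mg | 16800 mg | 1200 mg (7.1%) |
| 6 | 172 | 51600 mg | 50400 mg | 1200 mg (2.4%) |

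For the 200 mg cohort, Cycle 1 is 12800 against 11200 mg, a gap of 1600 mg. The percentages are the same.

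**3. A final cycle cut short.** This does not depend on N either. Every dose taken to day 14 of a later cycle gives 14 × 300 = 4200 mg. The per-cycle rule gives 4200/8400 = 50%. The on-study rule charges those 14 days 4200 mg, so the same days count there as fully dosed.

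**4. A fully adherent patient, on-study rule.** After c completed cycles, on calendar days, intensity = [N + 56(c − 1)] / [64 + 56(c − 1)]. With N = 57:

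- c = 1: 57/64 = 89.1%
- c = 2: 113/120 = 94.2%
- c = 6: 337/344 = 98.0%

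If days on treatment means dosing days (1 + 28 = 29 in Cycle 1), then 57/58 = 98.3% after Cycle 1 and 113/114 = 99.1% after two cycles.

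**5. Sensitivity to N.** The Cycle 1 per-cycle figure is N/56.

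| N | Cycle 1, per-cycle rule | On study after Cycle 1, calendar days | On study after 2 cycles, calendar days |
|---|---|---|---|
| 55 | 98.2% | 85.9% | 92.5% |
| 56 | 100.0% | 87.5% | 93.3% |
| 57 | 101.8% | 89.1% | 94.2% |
| 59 | 105.4% | 92.2% | 95.8% |
| 63 | 112.5% | 98.4% | 99.2% |

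The last row drops only one of 64 dosing slots. It is an arithmetic limit and fits poorly with section 6.11, which makes AUC to infinity a primary PK parameter.

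On calendar days the per-cycle rule needs N = 56 to give 100% in Cycle 1 and the on-study rule needs N = 64, so the two cannot both be right for the same patient.

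**The case against.** The strongest reply is that little depends on this ratio. Analyses are descriptive (section 6.1), no decision rule uses dose intensity, and section 6.12.1 also reports cycles received, dose delays, total dose taken and dose adjustments with reasons. A careful reader could tell a toxicity-driven reduction from an artefact of the denominator. That stands, and it limits the consequence. It does not make the stated formulas correct.

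A second reply is that 28 days may be a fair approximation for Cycle 1: at 56 scheduled doses the per-cycle figure is exact, and at 57 it is 1.8 points high. That stands too. A reader might infer that a fully dosed patient will appear over-dosed in Cycle 1, but this needs more than 56 scheduled doses. Section 5.1 modifies the cycle for sampling after repeated doses as well as after a single dose, so a further dose could be left out, and at 55 doses the patient appears slightly under-dosed.

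A reader might also infer that both formulas ignore the 32 days. Only the per-cycle one does.

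Finally, a reader might infer that the cohort with more early progressors will look less tolerant. That merges two effects. The 50% for a cut-short cycle arises only in the per-cycle summary, because the on-study denominator stops with treatment. The run-in effect is the same percentage in both cohorts and enters their comparison only if durations differ: on calendar days in the base case, 98.0 − 94.2 = 3.8 points between six and two completed cycles.

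**Conclusion.** The concern holds, and the SAP should be corrected. These are stated rules that give wrong figures if followed; they are not details left to the protocol.

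Two parts rest on no assumption about the Cycle 1 schedule: the 1200 mg or 1600 mg disagreement in Cycle 1 on calendar days, and the 50% score for a later final cycle fully dosed to day 14.

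The size of the on-study shortfall does rest on assumptions. With 57 Cycle 1 doses it is 10.9 points after Cycle 1 and 5.8 after two cycles on calendar days, but only 1.7 and 0.9 on dosing days. It fades as treatment continues. The undefined day count changes its size; in the base case neither reading removes it.

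The documents do not settle whether Cycle 1 intensity falls below or above 100% under the per-cycle rule, and they do not support a claim that the cohort comparison is biased in itself.

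**What to change.** Use one rule for both summaries in section 6.12.1.

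- **Per cycle:** the number of doses the protocol schedules for that patient from cycle start to the earlier of cycle end and treatment discontinuation, times the assigned dose. Doses withheld for toxicity stay in the denominator, as they do now, since section 6.12.1 deducts nothing for them.
- **On study:** the sum of the patient's cycle denominators, replacing the formula based on undefined days on treatment.
- **Cycle 1:** take the dose count from the protocol schedule and reconcile sections 5.1, 6.8 and 6.12.1 on it.

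As an illustration only, with 57 scheduled doses the Cycle 1 denominator would be 57 × 150 = 8550 mg or 57 × 200 = 11400 mg. A patient who took every scheduled dose would then score 100% in each cycle and on study.

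The cost is SAP wording and one derivation in the exposure dataset. No new data are needed and patient management does not change.

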6.12.2. Adverse Events

Adverse event (AE) terms and severity grades will be assigned by the investigator using Common Terminology Criteria for Adverse Events (CTCAE version 4.0, NCI 2009). In addition, AE verbatim text will also be mapped by the sponsor or designee to corresponding terminology within MedDRA. Adverse events will be reported using the following reporting process:

- The CTCAE Version 4 term reported by the investigator will be mapped to the MedDRA PT and system organ class (SOC) of the corresponding MedDRA lower level term (LLT), unless the reported CTCAE term is 'Other – specify'.
- If the reported CTCAE term is 'Other – specify' the MedDRA LLT, PT and SOC mapped from the verbatim AE term will be used.
- All listings and summaries will use the PT resulting from this process.

Pre-existing conditions are defined as AEs that begin prior to the first dose of study drug.

A treatment emergent adverse event (TEAE) is defined as any AE that begins between the day of first dose and 30 days after treatment discontinuation (or up to any time if serious and related to study treatment), or any pre-existing condition that increases in CTCAE grade between the day

of first dose and 30 days after treatment discontinuation (or up to any time if serious and related to study treatment). Comparisons of pre-existing conditions to on-treatment events at the LLT level will be used in the treatment-emergent computation.

A serious adverse event (SAE) is any AE during this study that results in one of the following outcomes:

- death
- initial or prolonged inpatient hospitalization
- a life-threatening experience (that is, immediate risk of dying)
- persistent or significant disability/incapacity
- congenital anomaly/birth defect
- considered significant by the investigator for any other reason.

Important medical events that may not result in death, be life-threatening, or require hospitalization may be considered SAEs when, based on appropriate medical judgment, they may jeopardize the patient and may require medical or surgical intervention to prevent one of the outcomes listed in this definition.

To assess the relationship of the AE to the study treatment, the following terminologies are defined (in Protocol Section 8.1.2):

- Related: a direct cause and effect relationship between the study treatment and the AE is likely.
- Possibly related: a cause and effect relationship between the study treatment and the AE has not been demonstrated at this time and is not probable, but is also not impossible.
- Unrelated: without question, the AE is definitely not associated with the study treatment.

As per Lilly's standard operating procedures (SOPs), all "related" and "possibly related" AEs and SAEs will be defined as related to study treatment.

The following TEAE/SAE listings and summaries will be produced:

- List of pre-existing conditions and AEs
- Overview of TEAEs
- Summary of TEAEs by PT (all grade and grade ≥ 3)
- Summary of TEAEs by SOC and PT (all grade and grade ≥ 3)
- Summary of TEAEs by PT and maximum grade (1-5)
- List of SAEs
- Summary of SAEs by SOC and PT (all grade and grade ≥ 3)
- List of DLT-equivalent toxicity.

The four summaries will be produced for all TEAEs/SAEs and repeated for TEAEs/SAEs related

to study treatment.

6.12.3. Deaths, Other Serious Adverse Events, and Other Notable Adverse Events

All deaths on study will be listed along with the reason for death, if known. A summary of deaths will also be produced.

6.12.4. Clinical Laboratory Evaluation

Laboratory data will be listed and summarized by each cohort. Abnormal results will be listed separately. In addition to the investigator reported adverse events, all relevant hematology, chemistry laboratory values, and hepatic monitoring test results will be graded according to CTCAE version 4.0. These derived values will be included on the listings of laboratory data and summary tables will be produced in a similar manner to those created for the investigator reported adverse events.

6.12.5. Vital Signs and Other Physical Findings

Temperature, blood pressure, pulse rate, respiration rate, weight and ECOG performance status will be listed and summarized for all patients on therapy.

6.12.6. Electrocardiograms

All electrocardiogram (ECG) data will be listed.

6.13. Protocol Violations

Protocol violations that can be derived from the data and are related to inclusion/exclusion criteria or treatment will be listed.

6.14. Annual Report Analyses

Annual report analyses, including Developmental Safety Update Report (DSUR) and Investigational Brochure (IB) analyses, are described in the LY2835219 Program Safety Analysis Plan.

6.15. Clinical Trial Registry Analyses

Additional analyses will be performed for the purpose of fulfilling the Clinical Trial Registry (CTR) requirements.

Analyses provided for the CTR requirements include the following:

Summary of adverse events, provided as a dataset which will be converted to an XML file. Both Serious Adverse Events and 'Other' Adverse Events are summarized: by treatment group, by MedDRA preferred term.

- An adverse event is considered 'Serious' whether or not it is a treatment emergent adverse event (TEAE).

- An adverse event is considered in the ‘Other’ category if it is both a TEAE and is not serious. For each Serious AE and ‘Other’ AE, for each term and treatment group, the following are provided:
 - the number of participants at risk of an event
 - the number of participants who experienced each event term
 - the number of events experienced.
- Consistent with www.ClinicalTrials.gov requirements, ‘Other’ AEs that occur in fewer than 5% of patients/subjects in every treatment group may not be included if a 5% threshold is chosen (5% is the minimum threshold).
- AE reporting is consistent with other document disclosures for example, the CSR, manuscripts, and so forth.

7. References

Cancer Therapy Evaluation Program, Common Terminology Criteria for Adverse Events, v4.0, DCTD, NCI, NIH, DHHS. 2009. Publish date: 29 May 2009.

